### 4.2 Per-Protocol Population

The per-protocol (PP) population for the crossover phase is a subset of the mITT population of the crossover phase and includes all mITT subjects without major protocol deviations that could impact the efficacy analyses. Subjects who are found to be <80% compliant with MS1819 during the crossover phase will be excluded from the PP population. The PP population will be used as supportive to the mITT population. Subjects will be included in the treatment sequence to which they were randomized regardless of the actual treatment sequence received.

The PP population for each stage of the extension phase is a subset of the mITT population of the extension phase and includes all mITT subjects without major protocol deviations that could impact the efficacy analyses. Subjects who are found to be <80% compliant with MS1819 during the relevant stage of the extension phase will be excluded from the PP population. The PP population will be used as supportive to the mITT population.

Prior to database lock, the protocol deviations will be reviewed and the PP Population will be determined for each phase.

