**Efficacy Sets**

- **Modified Intent-to-Treat Set (mITT):** All randomized patients receiving at least one dose of treatment and have at least one valid stool collection and CFA post baseline while receiving their assigned study drug. The primary analysis will be performed in the mITT set.
- **Per Protocol Set:** mITT patients completing both periods and without any major protocol deviation. A sensitivity analysis will be performed in the Per Protocol Set.

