### 10.3 Analysis Sets

- Safety Set: patients receiving at least one dose of treatment. Patients will be analyzed according to the treatment actually received. The Safety Set will be used for all analyses of safety endpoints unless specified otherwise and for the summaries of patients in listings related to dosing of study drug.
- Efficacy sets:
  - mITT Set: All randomized patients receiving at least one dose of treatment and have at least one valid stool collection and CFA post baseline while receiving their assigned study drug. The mITT set is considered as the primary set for the efficacy analysis. The mITT set will be used for all analyses of efficacy endpoints.
  - Per Protocol Set: Subset of the mITT set comprising all patients who do not violate the terms of the protocol in a way that would affect the study outcome significantly, as determined by the study clinician. Protocol deviations will be captured throughout the study and classified as minor or major and reviewed at a data review meeting before database lock. Attendees will include appropriate individuals from the Sponsor and contract research organization. Each major deviation will be categorized as either important or not important with respect to the effect on the primary endpoint analysis. A sensitivity analysis will be performed in the Per Protocol Set.

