## 7. MEASUREMENTS OF TREATMENT COMPLIANCE

Treatment compliance will be summarized separately for each dose of the crossover phase and each dose of the extension phase.

For the crossover phase, treatment compliance will be summarized for MS1819 in terms of mg/day using a compliance rate. Given that subjects were to take the dose associated with their pre-study PERT during treatment with PERT, detailed pill information was not collected and thus compliance rate for PERT will not be summarized.

The compliance rate for MS1819 for the crossover phase will be calculated as:

$$[\text{Actual Dose mg/day} / \text{Expected Dose mg/day}] * 100$$

The actual dose (mg/day) a subject received will be calculated as:

$$[(\text{number pills dispensed} - \text{number of pills returned}) * 280 \text{ mg}] / \text{number of actual study days on MS1819 in the crossover phase,}$$

where the number of actual study days on MS1819 is calculated as:

$$((\text{date/time of last MS1819 dose} - \text{date/time of first MS1819 dose}) / 86400) + 1.$$

The expected dose for MS1819 is either 2240 mg/day or 4480 mg/day, depending on the randomized treatment assignment.

Treatment compliance will be summarized by each study period and overall for MS1819 using descriptive statistics.

As described in Section 4.2, subjects found to be <80% compliant with MS1819 during the crossover phase will be excluded from the PP population for the crossover phase.

Individual data for study drug (number of capsules) dispensed and returned and treatment compliance will be listed for all subjects in the mITT population for the crossover phase.

For the extension phase, treatment compliance will be summarized for MS1819 in terms of mg/day using a compliance rate.

The compliance rate for MS1819 for the extension phase will be calculated as detailed above, replacing 280 mg with 140 mg for the dose of each capsule.

The expected dose for MS1819 is either 4480 mg/day (4.4 grams/day) or 6720 mg/day (6.7 grams/day), depending on the stage of the extension phase.

Treatment compliance will be summarized for the extension phase using descriptive statistics.

As described in Section 4.2, subjects found to be <80% compliant with MS1819 during a given stage of the extension phase will be excluded from the PP population for that stage of the extension phase.

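### The protocol defines the per-protocol set in two ways, and the SAP's 80% compliance cut does not catch patients who stop MS1819 early

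*SAP*

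**What the plan says.** Three places define the PP set:

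- **Protocol synopsis, Efficacy Sets:** "mITT patients completing both periods and without any major protocol deviation".
- **Protocol 10.3:** "all patients who do not violate the terms of the protocol in a way that would affect the study outcome significantly", as judged by the study clinician. Completion is not mentioned.
- **SAP 4.2:** the set "includes all mITT subjects without major protocol deviations that could impact the efficacy analyses". Completion is again not mentioned, but a numerical filter is added: "Subjects who are found to be <80% compliant with MS1819 during the crossover phase will be excluded from the PP population".

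SAP section 7 defines the compliance rate as actual mg/day over expected mg/day. Actual mg/day is capsules used × 280 mg, divided by study days on MS1819. Those days run from the first dose to the "date/time of last MS1819 dose", plus one. The expected amount is a daily rate, not a period total: "The expected dose for MS1819 is either 2240 mg/day or 4480 mg/day, depending on the randomized treatment assignment". No rate is calculated for PERT.

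Four other provisions matter:

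- SAP 4.1 admits a patient to the modified intent-to-treat (mITT) set on one valid CFA, in either period.
- SAP 9.1.1 leaves missing values missing.
- SAP section 1 lets the SAP prevail over the protocol where they differ.
- SAP section 11, which lists changes from the protocol, mentions only the dropped non-inferiority analyses.

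**The concern.** SAP 9.2.1.1 names the PP summary as the supportive look at the primary endpoint, and it is a table of CFA by treatment group. Without a completion condition, its MS1819 and PERT columns can hold different patients. Someone randomized to PERT first who then cannot stay on MS1819 counts in the PERT column only. Someone randomized to MS1819 first who leaves during PERT counts in the MS1819 column only.

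This dropout may not be random. Protocol 5.6.3 says that the OPTION patients who stopped during MS1819 did so mainly because their insufficiency symptoms increased. A reader would expect a compliance threshold to remove patients who took a few days of a three-week course. This one may not.

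**Working it through.** **1. The plan's own figures.** Protocol 7.3.1 allows for 20% withdrawal and enrols about 36 to obtain 30 completers: 30 × 1.2 = 36. (Dividing instead, 30 / 0.8 = 37.5, gives 38; the difference is immaterial here.) With 1:1:1:1 allocation (SAP 2.4), 36 / 4 = 9 patients per sequence at each dose. The capsule counts agree with the doses: 8 × 280 = 2240 mg and 16 × 280 = 4480 mg. A fully dosed day therefore equals the expected daily dose in both arms, and the dose cancels from the compliance rate.

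**2. Who passes the written rules.**

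- *PERT first, valid Visit 6 CFA, stops MS1819 in period 2:* in mITT through Visit 6. PP status depends on the compliance rate and the deviation review.
- *MS1819 first, valid Visit 6 CFA, leaves during PERT:* in mITT. MS1819 compliance is that of a completed period, so nothing numerical excludes the patient.
- *MS1819 first, quits before Visit 6 and leaves the study:* no CFA, so not in mITT and not at issue.
- *PERT first, withdraws before any MS1819 dose:* the rate is undefined, so the cut cannot be applied.

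**3. Compliance of a fully dosed patient who quits.** Let D be full dosing days and h the hours from the first to the last dose of a day. SAP days = (D − 1) + h/24 + 1 = D + h/24, so compliance = D / (D + h/24). The documents give no clock times. I assume a first dose at 08:00 and a last dose between 17:00 (h = 9) and 22:00 (h = 14).

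| Days before quitting | h = 9 | h = 14 | 80% cut |
|---|---|---|---|
| 1 | 72.7% | 63.2% | excluded |
| 2 | 84.2% | 77.4% | borderline |
| 3 | 88.9% | 83.7% | passes |
| 5 | 93.0% | 89.6% | passes |
| 10 | 96.4% | 94.5% | passes |

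Worked case: 3 / (3 + 9/24) = 3 / 3.375 = 88.9%. If whole dates were used instead of times, every row would be 100%.

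**4. How many patients.** In OPTION (Protocol 5.6.3), 5 of 41 enrolled stopped during MS1819 and 3 of 41 during PERT. Applied to 9 patients per sequence and dose:

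- PERT-only: 9 × 5/41 = 1.10 per dose. The chance of at least one is 1 − (36/41)^9 = 69% per dose, and 1 − (36/41)^18 = 90% over both doses.
- MS1819-only: 9 × 3/41 = 0.66 per dose.

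**5. Effect on the PERT mean.** OPTION PERT CFA had mean 86% and range 57–97%. Add one PERT-only patient to 15 completers averaging 86%:

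- at 57%: (57 − 86) / 16 = −1.8 points
- at 97%: (97 − 86) / 16 = +0.7 points

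A patient at the mean changes nothing. Two such patients give −58/17 = −3.4 to +22/17 = +1.3 points.

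**6. With planned days as denominator.** A 5-day quitter scores 5/16 = 31% (the 16-day minimum in Protocol 8.3.3.1) or 5/21 = 24% (three weeks), and is excluded either way.

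**The case against.** - **The SAP agrees with the protocol's statistical section.** This stands. A reader might infer that the SAP itself removed the completion condition. It did not: Protocol 10.3 already lacks it and SAP 4.2 follows. The contradiction lies inside the protocol, and the SAP settles it without comment.
- **The deviation review may remove these patients.** This also stands in part. Protocol 10.3 and SAP 4.2 and 5.2 provide for review before database lock, and stopping before the required 16 dosing days and missing Visit 9 could be classed as major there. So one cannot say that early stoppers will certainly remain in the PP set. However, no text makes early stopping a major deviation, and Protocol 7.3.4 lists withdrawal of consent and major deviations as separate reasons for removal. The outcome is left to judgement in an open-label trial.
- **The rate measures adherence while on drug; persistence is reported elsewhere.** True: SAP 5.1 and 8.2 cover disposition and time on treatment. But the same rate is used as a PP entry filter, and there it labels early stoppers compliant.
- **A PERT CFA taken before any MS1819 is a valid PERT value.** Correct. Dropping it leaves the MS1819 column unchanged and selects on tolerating MS1819. That cost is inherent in the synopsis definition.
- **The synopsis may not have meant a paired analysis.** A reader might infer that the PP set was intended as a within-patient check. The synopsis calls it only a sensitivity analysis, and the SAP plans crossover CFA summaries by treatment group without a paired difference.

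**Conclusion.** The concern holds as a contradiction that needs reconciling, together with a compliance rule that does not cover for it. On the written rules, a fully dosed patient who quits MS1819 from about day 3 onward passes the 80% cut. Day 2 depends on the assumed dosing hours, and a one-day quitter is excluded when date and time are used.

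The size is modest: about 1.1 PERT-only and 0.7 MS1819-only patients per dose, and −1.8 to +0.7 points on the PP PERT mean for one PERT-only patient. It would be tempting to quote 1.8 points as the bias, but that is the extreme case. Nothing in the documents says that patients who stop MS1819 absorb fat poorly on PERT.

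The counts assume that OPTION dropout, seen with a different capsule, carries over and applies equally in each sequence. Protocol 5.6.3 does not say in which sequence those patients stopped. The mITT primary summary is unaffected, and with the non-inferiority analysis dropped no formal conclusion changes.

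**What to change.** 1. In SAP 4.2 and Protocol 10.3, define PP as mITT patients with a valid CFA on assigned treatment at both Visit 6 and Visit 9 and no major deviation, in line with the synopsis. Alternatively, keep the looser definition, record and justify it in SAP section 11, and amend the synopsis to match.
2. For the 80% PP cut, compute expected intake over the planned MS1819 period days when a patient stops early, and to the actual end of the period for completers, so that days after a premature stop count as zero. State the planned number of days in the SAP. The denominator for stoppers should not run to the end of the stool collection, because they never reach one.

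The cost is a wording change and one programming change. The PP set loses about 1 to 2 patients per dose (1.10 + 0.66 ≈ 1.8). The missing MS1819 CFAs of early stoppers are not recovered, so the table should be read as a result in completers.

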### 4.3 Safety Population

The safety population for the crossover phase, which will be used for all safety analyses of the crossover phase unless stated otherwise, will include all randomized subjects who receive at least 1 dose of treatment. Subjects in the safety population will be analyzed according to the actual treatment received regardless of their randomized assignment.

The safety population for each stage the extension phase, which will be used for all safety analyses of the extension phase unless stated otherwise, will include all subjects that enroll into the extension phase and receive at least 1 dose of treatment in the relevant stage of the extension phase.

## 5. STUDY SUBJECTS

### 5.1 Disposition of Subjects

Disposition will be summarized separately for each dose of the crossover phase and each dose of the extension phase, unless stated otherwise.

The disposition of subjects will be summarized for all subjects screened in the study. The following disposition information will be summarized overall:

- The number of subjects screened.
- The number of subjects who failed screening and the reason for screen failure.

All percentages will use the number of screened subjects as the denominator.

The following disposition information will be summarized by treatment sequence for all subjects randomized in the study for the crossover phase:

- The number of subjects randomized.
- The number and percentage of subjects in the mITT population, PP population, and safety population.
- The number and percentage of subjects who completed the first treatment period (through Visit 6)
- The number and percentage of subjects who withdrew from the first treatment period and the reason for withdrawal
- The number and percentage of subjects who completed the second treatment period (through Visit 9)
- The number and percentage of subjects who withdrew from the second treatment period and the reason for withdrawal
- The number and percentage of subjects who completed the study (through Visit 10)
- The number and percentage of subjects who withdrew from the study and the reason for withdrawal

All percentages will use the number of randomized subjects as the denominator.

A data listing of subject disposition for all randomized subjects and a data listing of screen failures will also be provided for the crossover phase.

The following disposition information will be summarized for all subjects in the extension phase:

- The number and percentage of subjects in the mITT population, PP population, and safety population
- The number and percentage of subjects who were treated in the 2240 mg/day dose of the crossover phase

- The number and percentage of subjects who were treated in the 4480 mg/day dose of the crossover phase
- The number and percentage of subjects who were treated in both the 4.4 grams/day stage and the 6.7 grams/day stage of the extension phase
- The number and percentage of subjects who were treated in the 4.4 grams/day stage and not the 6.7 grams/day stage of the extension phase (4.4 grams/day summary only)
- The number and percentage of subjects who were treated in the 6.7 grams/day stage and not the 4.4 grams/day stage of the extension phase (6.7 grams/day summary only)
- The number and percentage of subjects who completed the extension phase treatment period
- The number and percentage of subjects who withdrew from the extension phase treatment period
- The number and percentage of subjects who completed the extension phase of the study (through Visit 17)
- The number and percentage of subjects who withdrew from the extension phase of the study and the reason for withdrawal

All percentages will use the number of subjects enrolled in the extension phase as the denominator.

A data listing of subject disposition for all subjects enrolled in the extension phase and a data listing of screen failures will also be provided for the extension phase.

## 5.2 Protocol Deviations

Protocol deviations will be summarized separately for each dose of the crossover phase (by treatment sequence) and each dose of the extension phase.

Protocol deviations will be identified on an ongoing basis by the study team.

The number and percentage of subjects with:

- at least 1 protocol deviation;
- at least 1 major protocol deviation;
- at least 1 protocol deviation for each protocol deviation type

will be summarized for the mITT population. For subjects that participated in both the crossover phase and the extension phase of the study, any protocol deviation that occurred prior to the start date of the extension phase will be summarized in the crossover phase. Any protocol deviation that occurred on or after the start date of the extension phase will be summarized in the extension phase.

Line listings will be provided to the study team for the manual classification of major vs. minor protocol deviations and the AzurRx study team will confirm classification of major vs. minor at a data review meeting prior to database lock. Each major deviation will be categorized as either important or not important with respect to the effect on the primary endpoint analysis for the crossover phase.

All subjects in the mITT population having a protocol deviation and the details for the protocol deviation will be identified in a subject-level data listing. The listings will include the date of the deviation, protocol deviation type, if it was IRB reportable, date reported to IRB, any noted comments, and the deviation corrective and preventative action (CAPA).

## 6. DEMOGRAPHIC AND OTHER BASELINE CHARACTERISTICS

Subject demographics and other baseline characteristics will be summarized descriptively by treatment sequence and overall for the mITT population separately for each of the doses in the crossover phase, and for each of the doses for the mITT population in the extension phase. The demographic and baseline characteristic summaries will be used to describe the study population as well as to check for balance among the treatment groups.

Demographic data for both the crossover and extension phases will include age, sex, race, and ethnicity. Age (years) will be age at screening, as collected on the CRF.

Baseline characteristic data for the crossover phase will include gastric acid suppression use at randomization, CFTR (cystic fibrosis transmembrane conductance regulator) modulator use at randomization (yes, no), name of pre-randomization PERT, pre-randomization PERT dose (lipase units/kg/day), weight, height, body mass index (BMI), and years since diagnosis of EPI. Pre-randomization PERT dose (lipase units/kg/day) will also be summarized by region.

Baseline characteristic data for the extension phase will include gastric acid suppression use at randomization, CFTR (cystic fibrosis transmembrane conductance regulator) modulator use at the start of the extension phase (yes, no), name of PERT used at the start of the extension phase, PERT dose at the start of the extension phase (lipase units/kg/day), weight at the start of the extension phase, height at the start of the extension phase, body mass index (BMI) at the start of the extension phase, and years since diagnosis of EPI.

Descriptive statistics (number of subjects, mean, SD, minimum, median, and maximum values) will be presented for continuous variables. For qualitative or categorical variables, the number and percentage of subjects within each category will be presented.

Individual data for demographics, baseline characteristics, and medical history will be presented in the data listings for subjects in the mITT population. A data listing of any inclusion/exclusion criteria not met will also be presented for all screened subjects.

Partial missing dates will be imputed for the purposes of determining time since diagnosis of EPI as follows:

- For a partially missing diagnosis date where the day is missing, but the month and year are present, the day will be set to the first day of the month.
- For a partially missing diagnosis date where the day and the month are missing, but the year is present, the month and day will be set to January 1st.

Years since diagnosis of EPI will be calculated in years using the imputed diagnosis date and the date of randomization as  $[(\text{date of randomization} - \text{diagnosis date})/365.25]$ , rounded to one decimal place.

## 7. MEASUREMENTS OF TREATMENT COMPLIANCE

Treatment compliance will be summarized separately for each dose of the crossover phase and each dose of the extension phase.

For the crossover phase, treatment compliance will be summarized for MS1819 in terms of mg/day using a compliance rate. Given that subjects were to take the dose associated with their pre-study PERT during treatment with PERT, detailed pill information was not collected and thus compliance rate for PERT will not be summarized.

The compliance rate for MS1819 for the crossover phase will be calculated as:

$$[\text{Actual Dose mg/day} / \text{Expected Dose mg/day}] * 100$$

The actual dose (mg/day) a subject received will be calculated as:

$$[(\text{number pills dispensed} - \text{number of pills returned}) * 280 \text{ mg}] / \text{number of actual study days on MS1819 in the crossover phase,}$$

where the number of actual study days on MS1819 is calculated as:

$$((\text{date/time of last MS1819 dose} - \text{date/time of first MS1819 dose}) / 86400) + 1.$$

The expected dose for MS1819 is either 2240 mg/day or 4480 mg/day, depending on the randomized treatment assignment.

Treatment compliance will be summarized by each study period and overall for MS1819 using descriptive statistics.

As described in Section 4.2, subjects found to be <80% compliant with MS1819 during the crossover phase will be excluded from the PP population for the crossover phase.

Individual data for study drug (number of capsules) dispensed and returned and treatment compliance will be listed for all subjects in the mITT population for the crossover phase.

For the extension phase, treatment compliance will be summarized for MS1819 in terms of mg/day using a compliance rate.

The compliance rate for MS1819 for the extension phase will be calculated as detailed above, replacing 280 mg with 140 mg for the dose of each capsule.

The expected dose for MS1819 is either 4480 mg/day (4.4 grams/day) or 6720 mg/day (6.7 grams/day), depending on the stage of the extension phase.

Treatment compliance will be summarized for the extension phase using descriptive statistics.

As described in Section 4.2, subjects found to be <80% compliant with MS1819 during a given stage of the extension phase will be excluded from the PP population for that stage of the extension phase.

Individual data for study drug (number of capsules) dispensed and returned and treatment compliance will be listed for all subjects in the mITT population for the extension phase.

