## 8.2 Extent of Exposure

Time on treatment (weeks) will be calculated as (date of last dose of study drug – date first dose of study drug + 1)/7. Time on treatment will be summarized by treatment group for each period using descriptive statistics for all subjects in the safety population for the crossover phase. Time on treatment will be summarized using descriptive statistics for all subjects in the safety population for each dose in the extension phase. For subjects that participated in both the 4.4 grams/day period and the 6.7 grams/day period of the extension phase, time on treatment will also be summarized across both doses. Total time on treatment for MS1819 (across both doses of each the crossover phase and the extension phase) will also be summarized.

The date and time of the first and last dose of each study period will be presented in a data listing for all subjects in the safety population for each dose in the crossover phase. The date and time of the first and last dose will be presented in a data listing for all subjects in the safety population for each dose in the extension phase.

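### The MS1819 compliance formula adds a whole day to an elapsed time, so patients who miss no dose score a few points below 100% and the 80% per-protocol cut is somewhat stricter than stated

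*SAP*

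**What the plan says.** SAP Section 7 defines MS1819 compliance as actual mg/day over expected mg/day. Actual mg/day is capsules dispensed minus returned, times capsule strength, divided by the days on MS1819, "where the number of actual study days on MS1819 is calculated as" the date/time of the last dose minus the date/time of the first, converted from seconds to days, with 1 added. The expression ends "date/time of first MS1819 dose}) / 86400) + 1" (the curly bracket is a typesetting remnant).

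The comparator is a full day's dose: "The expected dose for MS1819 is either 2240 mg/day or 4480 mg/day, depending on the randomized treatment assignment". The extension uses the same calculation, "replacing 280 mg with 140 mg for the dose of each capsule", against 4480 or 6720 mg/day.

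The rate decides PP membership. SAP Section 4.2: "Subjects who are found to be <80% compliant with MS1819 during the crossover phase will be excluded from the PP population". The same rule applies to each extension stage. Section 4.2 also makes the PP set supportive to the mITT set and fixes its membership before database lock.

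SAP Section 8.2 counts exposure differently. "Time on treatment (weeks) will be calculated as" the last date minus the first date plus 1, over 7, with no clock time.

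**The concern.** Adding 1 is the usual correction for a difference between calendar dates, where the first day would otherwise be lost. The divisor of 86,400 shows that Section 7 works in seconds, so the interval already carries its part-days. What it leaves out is not a whole day of dosing.

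Part-days are normal here. MS1819 is dispensed at a clinic visit (Protocol 8.2, Visit 3), and the switch comes as soon as the second dye marker has passed (Protocol 8.3). First and last doses can therefore fall at any meal or snack.

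At stake is whether the compliance table reads correctly, and whether a patient who truly meets the 80% standard can be dropped from the PP set. One patient is 11% (1/9) of the initial extension cohort.

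**Working it through.** **The plan's own figures.** Expected dose is capsules per day times strength (Protocol Tables 2 and 4): 8 × 280 = 2240, 16 × 280 = 4480, 32 × 140 = 4480, 48 × 140 = 6720 mg/day. All match SAP Section 7, so the comparator is sound and only the day count is in question.

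**Inputs.**
- Dose split: 1/4 at each of three meals, 1/8 at each of two snacks (Protocol 7.4 and 11.4.4.1).
- Calendar days on drug, N, crossover: confinement from Day 17 (+5), second marker on confinement Day 4, stay up to 7 days (Protocol Table 1 and 8.3.3.1). This gives about 20 to 28.
- N, extension: confinement from E11 (+4) with the same stay (Protocol Table 3), giving about 14 to 21.
- Assumption: breakfast 08:00 and dinner 19:00, so 11 hours or 0.458 day. Dosing days of 6 to 16 hours were also tried.

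**Formula.** For a patient who misses nothing, let A be the daily doses taken from first to last dose and T the elapsed days. The SAP score is A/(T + 1), and the true compliance needed to reach a score of 80% is 0.80 ÷ score.

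| First → last dose | N | A | T + 1 | Score | Effective cut |
|---|---|---|---|---|---|
| Breakfast → dinner | 21 | 21 | 21.458 | 97.9% | 81.7% |
| Breakfast → breakfast | 21 | 20.25 | 21 | 96.4% | 83.0% |
| Dinner → breakfast | 21 | 19.5 | 20.542 | 94.9% | 84.3% |
| Breakfast → dinner | 14 | 14 | 14.458 | 96.8% | 82.6% |
| Breakfast → breakfast | 14 | 13.25 | 14 | 94.6% | 84.5% |
| Dinner → breakfast | 14 | 12.5 | 13.542 | 92.3% | 86.7% |

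The breakfast-to-breakfast rows need only the same clock time on both days, not the 11-hour assumption.

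**Why neither 1 nor 0 is right.** The end correction that gives 100% is A − T. Over 21 days it is 21 − 20.458 = 0.54 for breakfast to dinner, 20.25 − 20 = 0.25 for breakfast to breakfast, and 19.5 − 19.542 = −0.04 for dinner to breakfast.

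**Sensitivity.** For breakfast-to-last-meal dosing, a dosing day of 6 to 16 hours gives 98.8% down to 96.9% (21 days) and 98.2% down to 95.5% (14 days). Across 300,000 random sets of fixed meal times, the highest score was 99.7%. Over all first/last meal pairs, N = 20 gives 94.7–97.8% and N = 28 gives 96.2–98.4%.

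**What misclassification looks like.** Take a 14-day stage at 4.4 g/day with a dinner start and breakfast stop. Capsules scheduled are 8 + 12 × 32 + 8 = 400. A patient who takes 340 has 85% compliance, but the SAP gives 340 × 140 ÷ 13.542 ÷ 4480 = 78.5%, and the patient is excluded.

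**The alternatives.**
- Delete the added 1: breakfast to dinner gives 21/20.458 = 102.6% and 14/13.458 = 104.0%, moving the cut to 77.9% and 76.9%. Dinner to breakfast gives 99.8% and 99.7%.
- Use the date-only count of Section 8.2: full-day patients score 100%, but dinner to breakfast gives 19.5/21 = 92.9% and 12.5/14 = 89.3%, lower than now.
- Capsules taken over capsules scheduled between first and last dose: 100% in every row, and the cut is 80%.

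**The case against.** The strongest reply is that some end correction is needed, so the added 1 is not simply surplus. For a full-day patient the raw interval is about 0.54 day too short, while the SAP's is about 0.46 day too long. This is right, and it is why deleting the 1 is not the remedy. Section 8.2 is not a ready model either, since its date-only count does worse for late starters who stop early.

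A reader might infer that every compliant patient must score below 100%. The documents do not support that, for three reasons:
- Unreturned capsules count as taken. For a breakfast-to-dinner patient, 0.458 of a day's capsules cancels the shortfall: about 4 or 7 in the crossover, 15 or 22 in the extension.
- If only dates are recorded, full days score 100%.
- Protocol Tables 2 and 4 allow individual variation. A patient who fits the full daily total into both the first and the last day, and whose last dose is at an earlier clock time than the first, can score 100.2–100.6%, though that pattern is contrived.

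A reader might also take 87% as the general extension cut. It needs the minimum 14-day stage plus a dinner start and a breakfast stop. At 21 days the extension and crossover effects are the same.

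Finally, the PP set is supportive, efficacy is primarily mITT, all efficacy summaries are descriptive, and SAP Section 11 drops the non-inferiority analysis. Nothing in the documents suggests that anyone will fall in the affected band. All of this stands. It limits the consequence but does not make the formula right.

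**Conclusion.** The point holds as a small arithmetic fault. With recorded clock times and doses spread over five occasions, Section 7 understates the compliance of a patient who misses nothing by about 2 to 5 points over 21 days and 3 to 8 points over 14 days. The stated 80% cut then acts as about 82–84% and 83–87% respectively, the upper ends being worst cases. The 11-hour dosing day is an assumption; other dosing days change the size but not the direction.

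A reader might infer that fully compliant completers are being removed, or that the primary result is at risk. Neither follows. The lowest score for a fully compliant patient at the 14-day minimum is 92.3%, so only true compliance just above 80% can be misclassified. A patient who misses nothing falls below 80% only after about 5 days or fewer on MS1819: 3.5/4.542 = 77% for a dinner start and breakfast stop over 5 calendar days. In the crossover that would be an early withdrawal who is in the mITT set through the PERT period. The damage is confined to the compliance table and the supportive PP summaries.

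**What to change.** In SAP Section 7, for both phases, replace the day-count denominator with the capsules scheduled between the first and last recorded MS1819 dose:

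Compliance (%) = 100 × (capsules dispensed − capsules returned) ÷ capsules scheduled.

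Full days count 8 or 16 capsules (crossover) or 32 or 48 (extension). The first and last days are prorated by the typical fractions in Protocol Tables 2 and 4. Apply the 80% cut to this rate. Do not simply delete the added 1, and do not copy the date-only count from Section 8.2.

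The cost is one SAP formula and its programming, made before PP membership is fixed at the pre-lock review. The small downside is that expected capsules on part-days come from the typical schedule although individual variation is allowed. Protocol Table 1 and Table 3 call for study drug to be recorded at every meal and snack in confinement, which helps for the last day. A short rule for assigning the first dose to a meal or snack would cover the other end.
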